9.3 Surgical data and robotic-assisted surgery session files

Legal agreements are in place between Stryker and the RDUH to protect participants' identity and personal information will be held confidentially in accordance with GDPR. These protections will remain even if data is transferred outside the EU, such as to the USA. Stryker will hold data from previously received CT scans for the purposes of planning the surgery, and could potentially use it for linkage of with the session files and surgery data. However, there will be strict contracts in place to ensure data confidentiality is maintained. This data sharing has already been approved by RDE Governance and is already currently occurring for patients undergoing MAKO THRs as part of routine clinical practice.

9.4 Data collection processes

The pre-, peri-, and post-operative data collection will be completed by members of the site Research Team. Surgical parameters and results of blood biomarkers will be collected from participant medical notes via EPIC, which constitutes source data, and PROMs data will be completed directly onto the REDCap database by the participant.

Physical activity monitoring data will be collected by members of the site Research Team with additional support provided by the Trial Manager and the Co-CI. Activity monitoring data will be uploaded and stored locally, and transferred pseudonymously to members of the University of

Exeter Research Team (Co-CI) for processing. The Co-CI has led previous trials using ActivInsights activity monitors at the RDE, and will process the activity data to collect the specific activity outcome measures that will be used in this trial. These outcomes will be securely transferred to ExeCTU to store on the same secure database as all other outcome measures.

9.5 Data access

Access to data held at the participating site will be restricted to those holding a substantive or honorary contract for the RDE and who have a relevant purpose to access the data. Access will be granted to authorised representatives from the RDUH NHS Foundation Trust as the Sponsor, as well as representatives from the UoE for the purposes of auditing and monitoring the trial.

Participants will be asked to consent to representatives of the Sponsor or the UoE accessing their data that is relevant to their participation in the trial.

Data entered into the EDC system will be accessed by authorised members of the trial team at the participating site and at ExeCTU. Access will be restricted with individual log-in credentials, and site and role restriction applied so that individuals can only access data appropriate to their location and role.

9.6 Data shared with third parties

De-identified data that underlie the results reported in the trial will be deposited in the University of Exeter's Open Research repository and available for non-commercial use, on a controlled access basis, subject to suitable data requests and data sharing agreements. Data may be used for commercial purposes, according to the conditions above, but will need specific agreements in place prior to access being agreed. This may include a license fee.

9.7 Archiving

The Sponsor is responsible for arranging appropriate archiving on conclusion of the trial of the TMF and EDC system data. The RDE will be responsible for archiving their investigator site file, including paper consent forms and any paper PROMs, following the local NHS Trust archiving procedure.

Trial documentation and data will be archived for at least 10 years following the completion of the trial, as per local NHS Trust SOP.

10 MONITORING, AUDIT AND INSPECTION

A detailed monitoring plan will be agreed between the CI and Co-CI, ExeCTU and the Sponsor. The monitoring plan will be based on the risk assessment that will be reviewed periodically and in response to amendments to the trial protocol.

Monitoring will be conducted by a combination of remote and central monitoring led by ExeCTU. On-site monitoring will be conducted if one or more triggers are met, as detailed in the monitoring plan, or if concerns are raised by an individual with knowledge of the trial. The RDE will be expected to cooperate with remote and onsite monitoring procedures by provision of copies of requested documents in a timely manner and the completion of self-audit checklists. In the case of triggered on-site monitoring visits, the RDE will be expected to provide space for the monitor(s) to work on the NHS Trust premises and provide access to all documents requested in the notification of monitoring visit letter. The CI or delegated member of the site Research Team must be available during on-site monitoring visits. ExeCTU will provide the RDE with sufficient notice to prepare for a

monitoring visit. The Sponsor and/or regulatory authorities may audit or inspect any aspect of the trial, including ongoing site visits, at any time during the trial.

The DMC will review data completeness, data quality and accumulating safety data at agreed intervals throughout the trial.

11 ETHICS AND REGULATORY APPROVALS

11.1 Research Ethics Committee (REC) review and reports

The research will be performed subject to favourable opinion from a UK NHS REC and HRA, and local site capacity and capability confirmation from the Research and Development department. Ethics review of the protocol for the trial and other trial-related essential documents (e.g. PIS and consent form) will be carried out by an NHS REC. Any subsequent amendments to these documents will be submitted to the REC and HRA for approval prior to implementation.

The trial will be conducted in compliance with the principles of the Declaration of Helsinki and to Good Clinical Practice (GCP) guidelines. All data will be stored securely, and will be stored in accordance with current legislation. The trial will be registered with ISCRTN before the first participant is recruited.

Annual reports will be submitted to the REC within 30 days of the anniversary date on which the favourable opinion was given, and annually until the trial is declared ended. The REC and trial Sponsor will be notified of the end of the trial (whether the trial ends at the planned time or prematurely).

The CI will submit a final report to the REC and HRA with the trial results, including any publications, within one year of the end of the trial.

11.2 Risks and benefits to trial participants

The eligibility criteria ensure that all trial participants require, and would normally have, one of the three trial options (SPAIRE, PSPA or PA) as routine treatment for their THR. Participants will also undergo pre-operative X-ray and CT imaging and post-operative X-ray imaging as part of their routine care. In general, therefore, the trial will not expose participants to risks additional to standard of care.

11.3 Public and patient involvement and engagement (PPIE)

The Exeter Hip Unit established a PPIE group during the development of this trial proposal, which included both patients and carers. Potential outcomes measures for the trial were explored by the Research Team through a PPIE workshop, facilitated by the Public Involvement team of the South-West Research Design Service, to explore patient and carer experiences of THR. The PPIE group was introduced to the overall research objective: to understand whether tendon-sparing approaches might improve the patient experience of THR. Outcome measures, including PROMs, performance outcome measures, and functional outcome measures, were discussed to identify the most suitable primary and secondary endpoints with which to assess the efficacy of the PSPA and SPAIRE approach compared with the standard PA.

Based on the feedback from the PPIE group, several outcome measures were identified for potential inclusion, in addition to the outcome measures collected as part of routine care:

- Hip abduction strength
- Hip external rotation strength
- Walking step rate and bout length

- Sleep quality
- Lower extremity function scale PROM

This PPIE workshop, combined with pilot studies and additional PPIE consultation, led to the identification of the OARS PROM as a suitable primary outcome measure, and secondary outcome measures that will provide additional measures of efficacy of the PSPA and SPAIRE approach compared with the PA.

Several attendees of the PPIE workshop were also recruited to provide feedback on the trial proposal lay summary, and have agreed to provide similar feedback on Patient Information Sheets during the trial.

Further involvement and engagement will be completed during the trial. When patients are enrolled into the trial, they will be asked whether they would like to be kept informed about developments of the trial, and whether they would be interested in attending PPIE events. This will allow the Research Team to send trial updates via an email newsletter (or by post when requested), and ensure that participants have the opportunity to attend engagement events at least once a year.

PPIE will also occur throughout the trial through membership of the TMG, and the TSC.

11.4 Regulatory compliance

Recruitment will commence at site once the RDE Research and Development department has confirmed capacity and capability to deliver the trial.

The latest HRA guidance will be followed at all times with regard to notification and implementation of amendments at sites.

11.5 Protocol compliance

All staff undertaking research activities outlined in the protocol will be trained prior to commencing work on the trial. The eCRFs and EDC system will be designed to assist in adherence to the protocol by guiding trial personnel through the assessments and data collection. The EDC system will also be validated to minimise protocol deviations. The site Research Team will be trained to notify the Trial Manager in the event of a protocol deviation or suspected or actual serious breach, by reporting directly to ExeCTU through REDCap. A deviation log will be maintained in REDCap by ExeCTU and reviewed regularly by the CI, Co-CI and the Sponsor. Recurrent deviations will be discussed with the TMG and TSC, as appropriate. The Trial Manager will work with the site Research Team to identify the cause of the deviations and put in place steps to mitigate them, as appropriate. Protocol compliance will be reported at the end of the trial.

11.5.1 Notification of serious breaches to GCP and/or the protocol

A serious breach is a breach that is likely to affect:

- (a) the safety or physical or mental integrity of the participants of the trial; or
- (b) the scientific value of the trial

All suspected serious breaches will be notified to the Sponsor by a member of the ExeCTU trial team within 24 hours of becoming aware of the breach, in accordance with the ExeCTU SOP. The RDE site will notify ExeCTU of the suspected serious breach in the first instance by reporting directly onto REDCap. The suspected breach will be logged on the ExeCTU Quality Management System (QMS). The Sponsor representative will decide if the event constitutes a serious breach, and if so will report to the REC within 7 days of becoming aware as per the REC SOP. In the event of a serious breach, the Sponsor, ExeCTU and the individuals involved will work together to

agree and implement a Corrective and Preventative Action (CAPA) plan and follow up on the plan at agreed intervals to ensure effective implementation.

11.6 Conflicts of interest

There are no competing interests associated with this trial. The trial is aiming to identify whether tendon-sparing approaches for THR lead to better patient outcomes, but there is no intellectual property associated with the approaches used in the trial.

Members of the surgical team ([name], [name], [name], [name], [name] and [name]) do have commercial ties with Stryker, who manufacture and distribute the THR devices and MAKO robotic guidance system that will be used in the trial. However, all surgical interventions used in the trial will adopt the same medical devices and surgical guidance system, and no member of the surgical team will be involved in the collection or analysis of outcome measures at any time point, and therefore, will not have any influence over the evaluation or reporting of trial results.

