3.4.4 Clinical outcome measures

Clinical outcome measures include length of hospital stay, surgery time, blood loss and analgesic use. Analgesic use is defined as the quantity and duration of analgesia required in the immediate period 6 weeks post-operation. Participants will be discharged from hospital with a routine, set amount of analgesia as per hospital protocols. These medications are listed below:

- 12 days of Paracetamol 1g
- 5 doses of twice daily Celecoxib 200mg
- 5 doses of 10mg Oxycodone MR to be used twice a day
- 5 doses of 5mg Oxycodone IR to be used as required (and maximum four times a day)
- 5 days of 30mg Codeine Phosphate to be used as required and maximum 4 times a day (once Oxycodone course has finished)

Participants will be asked at their 6 week post-operative visit if any additional analgesia, in addition to the above prescription, was used immediately post-surgery up to 6 weeks post-operatively, either purchased over-the-counter without prescription or via GP prescription. This will be a yes/no answer, and the site Research Team will record the names of any additional analgesia in a free text box in the eCRF. Doses of analgesia will not be collected as patient recall is likely to be inaccurate, according to our PPIE representatives on the TMG.

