6.7.4 Peri-operative time point

- Retrospective data collection from participant medical notes review on EPIC and subsequent entry into REDCap for:
- Surgery time this will be defined from the time that surgical incision was made through to time that the wound dressing was applied at the end of the surgical procedure
- Blood loss this will be an estimate of blood loss (mls) made by the surgical and anaesthetic teams
- If there has been a conversion from allocated randomised approach this will be documented and the reason for conversion also documented

Report any AEs/SAEs that have occurred during surgery.

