At the discretion of the CI, participants may be withdrawn from randomised surgery and/or from follow-up data collection if it is felt in their best interest to do so. Prior to surgery, if other surgeons have an opinion that participants need to be withdrawn from randomised surgery this would need to be discussed with the CI prior to the CI making a final decision on withdrawal.

For randomised participants, all data collected up to the point of change in their participation status or withdrawal will be retained and used in the analysis. Participants who withdraw before randomisation will not be included in the final analysis. If the THR was not performed as scheduled

for unexpected reasons such as bed shortages, industrial action, staffing issues, participant short term medical issues (e.g. acute respiratory or urinary infections just prior to surgery) etc then the participant's' surgery would be rescheduled to the next available appropriate time as close as possible to the original surgical date.

For individuals who have provided informed consent, but who later lose capacity during the trial the following process will apply; the consent obtained prior to loss of capacity will not endure the loss. The participant will stop their participation but data already collected up to the point of loss of capacity will be retained and will be used in analysis.

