7.2.2 Non-reportable adverse events

Some events which occur during treatment and recovery will be considered normal aspects of the anaesthetic and post-operative recovery process, and that occur frequently after surgery. They will not need reporting as AEs, unless in the opinion of the CI are untoward, excessive, or outside of what might normally be expected for the procedure, or fall into the category of an SAE. These include:

- Nausea and/or vomiting after surgery
- Drowsiness or headache after surgery
- Temporary low blood pressure after surgery
- Sore throat after surgery
- Itching after surgery
- Post-operative pain (note that this will be collected as an outcome) unless this is considered abnormal by the treating clinical team
- Memory loss or confusion during the hospital stay only, or which the treating clinician believes is due to analgesics
- Numbness on the lateral side of the surgical wound
- Early wound oozing which spontaneously resolves
- Bruising, unless this is considered abnormal by the treating clinical team
- Mild discomfort during or immediately after physiotherapy (inpatient and outpatient).

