7.2.4 Causality

Causality of reportable SAEs will be assessed by the CI (in their role as site PI) or authorised delegate), see table 2. All SAEs which are possibly, probably or definitely related to the intervention will be categorised as 'related'. If the CI or delegate is unable to assign causality within 24 hours of the site becoming aware of the event, the SAE will be treated cautiously and subjected to expedited reporting (see section 7.3 below).

Table 2: The causality of SAEs (i.e. relationship to trial treatment) will be assessed by the site PI (or delegate) using these descriptions:

Relationship to trial procedure	Description
Unrelated	There is no evidence of any causal relationship
Unlikely to be related	There is little evidence to suggest there is a causal relationship (e.g. the event did not occur within a reasonable time after administration of the trial intervention). There is another reasonable explanation for the event (e.g. the participant's clinical condition, other concomitant treatment)
Possible relationship	There is some evidence to suggest a causal relationship (e.g. because the event occurs within a reasonable time after administration of the trial intervention). However, the influence of other factors may have contributed to the event (e.g. the participant's clinical condition, other concomitant treatments)
Probable relationship	There is evidence to suggest a causal relationship and the influence of other factors is unlikely
Definitely related	There is clear evidence to suggest a causal relationship and other possible contributing factors can be ruled out

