7.3 Reporting adverse events

All reportable AEs/SAEs/RUSAEs should be recorded from the point of surgery to the end of trial participation at 12 months (52 weeks) follow-up post-operatively.

SAEs must be reported directly onto REDCap **within 24 hours** of the blinded site Research Team becoming aware of the event. SAEs classed as possibly, probably or definitely related AND unexpected (RUSAEs) will be reported by ExeCTU to the Sponsor within 24 hours of ExeCTU staff becoming aware. The Sponsor is responsible for onward reporting of RUSAEs to the REC within 15 days of the event being reported to ExeCTU in REDCap. However, if the event results in death the SAE will be reported to the REC within 7 days of the event being reported to ExeCTU in REDCap.

The CI (in their role as site PI) or their delegate, is responsible for signing off reportable SAEs within the EDC system. This will be a role restricted task that only authorised users of the EDC can complete.

For each SAE the following information will be collected:

- full details in medical terms and case description
- event duration (start and end dates, if applicable)
- action taken
- outcome
- seriousness criteria
- causality (i.e. relatedness to intervention)

Any change of condition or other follow-up information should be updated directly onto REDCap as soon as it is available. Events will be followed up until the event has resolved or a final outcome has been reached. An outcome of 'unknown' is not considered to be an acceptable final outcome. An outcome of 'not yet resolved' is an acceptable final outcome for non-serious AEs at the end of a participant's involvement in a trial, and for SAEs at database lock.

Where SAE causality is initially assessed by an authorised delegate of the CI but not the CI themselves, the CI (in their role as CI, as opposed to site PI) will record a second assessment of causal relationship. The CI may upgrade the causality assessment (e.g. from not related to related) but may not downgrade the assessment (e.g. related to not related). Where a causal relationship is suggested, the CI will record an assessment of expectedness.

The TSC and DMC will periodically review SAE data to determine patterns and trends of events, or to identify safety issues, which would not be apparent on an individual case basis.

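### Section 11.6 says the surgical team has no part in collecting outcome measures, but the unblinded theatre teams estimate blood loss, and no rule keeps an operating surgeon from rating SAE causality

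*Protocol*

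**What the plan says.** Section 11.6 declares that members of the surgical team have commercial ties with the manufacturer of the devices and the robot. It gives two reassurances. All arms use the same devices and guidance system, and "no member of the surgical team will be involved in the collection or analysis of outcome measures at any time point". From the second it concludes that the team "will not have any influence over the evaluation or reporting of trial results".

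Other sections describe what happens in practice:

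- Section 3.4.4: "Clinical outcome measures include length of hospital stay, surgery time, blood loss and analgesic use". Sections 3.2 and 3.5 also list blood loss as a secondary outcome.
- Section 6.7.4, on blood loss: "this will be an estimate of blood loss (mls) made by the surgical and anaesthetic teams".
- Section 6.6: the operating surgeon receives the allocation by email within 24 hours of surgery and passes it to the theatre team.
- Section 7.2.4: "Causality of reportable SAEs will be assessed by the CI (in their role as site PI) or authorised delegate".
- Section 7.3 provides a second causality rating only in one situation: "Where SAE causality is initially assessed by an authorised delegate of the CI but not the CI themselves, the CI" records a further assessment, which may raise but not lower the delegate's rating.
- Section 6.8, on withdrawal before surgery: "if other surgeons have an opinion that participants need to be withdrawn from randomised surgery this would need to be discussed with the CI". The wording implies that the CI is also a surgeon.

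**The concern.** The statement in Section 11.6 is unqualified. It covers every member of the surgical team, every outcome measure and every time point, and the protocol relies on it as a safeguard. A reader of the trial report would take it to mean that every outcome was produced independently of the people who knew and performed the approach.

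For blood loss that is not so. The value is a judgement made by people who know which approach was used and may expect less tissue damage from the newer ones. A result of lower blood loss with PSPA or SPAIRE could not be cleanly separated from that expectation.

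For safety, relatedness is also a judgement. It matters because the Trial Summary frames the safety objective around related events, and because Section 7.3 makes relatedness, together with unexpectedness, the trigger for reporting to the ethics committee.

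**Working it through.** The plan states no figure on this point, so the check is mainly a comparison of sections.

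**Blood loss**

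1. Is it an outcome measure? Yes (Sections 3.2, 3.4.4 and 3.5).
2. Who produces the value? The surgical and anaesthetic teams, by estimate (Section 6.7.4). Research staff later copy it from the notes into the database (Sections 6.7.4 and 9.4). Copying does not change who made the estimate.
3. Do they know the allocation by then? The operating surgeon and theatre team do (Sections 6.5 and 6.6). Anaesthetic staff are not named separately; I take them to be part of the theatre team. The surgeon's knowledge is enough for the point.
4. Does Section 11.6 allow for this? No. It has no exception, and its phrase about time points takes in the operation itself. Section 6.6 has a narrower safeguard, covering operating surgeons and post-operative data only. That is compatible with an intra-operative estimate; Section 11.6 is not.

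**SAE causality**

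1. Are adverse events an outcome? Yes (Section 3.5).
2. Who rates causality? The CI acting as site PI, or an authorised delegate (Section 7.2.4).
3. Is the rater required not to have operated on the participant, or to be unaware of allocation? No section says so.
4. Is there a second rating? Only if a delegate rated first (Section 7.3). If the CI rates first, that single rating stands.

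**Illustration of what shading could do to the blood-loss comparison (assumed shifts)**

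Inputs from the protocol:
- 339 participants in three equal arms, so 339/3 = 113 per arm (Sections 6.5 and 8.1). Section 8.6.3 assumes no missing blood-loss data.
- A two-sided threshold of 0.025 for secondary outcomes (Section 8.6.1), giving a critical value of 2.241.

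Assumed: no true difference, a simple unadjusted two-group comparison, and a uniform shift of b SD in one arm's estimates.

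The standard error of the difference, in SD units, is sqrt(2/113) = 0.1330. The chance of p<0.025 is

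P = Φ(b/0.1330 − 2.241) + Φ(−b/0.1330 − 2.241).

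| Assumed shift b | b/0.1330 | Chance of p<0.025 |
|---|---|---|
| 0 | 0 | 0.025 |
| 0.1 SD | 0.752 | 0.070 |
| 0.2 SD | 1.503 | 0.230 |
| 0.3 SD | 2.255 | 0.505 |

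Nothing in the documents shows that any such shift occurs or how large it would be. The table says only that a modest shift, if shared across surgeons, would not be harmless at this sample size.

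**The case against.** **Collection belongs to the research team.** Section 9.4 gives pre-, peri- and post-operative data collection to site research staff working from the medical record. On that usage surgeons create source notes and others collect. This stands as an account of who transcribes. It does not rescue Section 11.6, which goes on to claim that the surgical team has no influence over evaluation.

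**The commercial ties favour no arm.** All arms use the same devices and robot. This stands. What remains is the ordinary problem of an unblinded operator's expectations about the approach. Operator unblinding is unavoidable here and is openly stated in Section 6.6.

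**The safety part is well protected.** Much of this stands. Blinded staff enter SAEs, the CI cannot lower a delegate's rating, and the DMC and TSC review SAE data (Section 7.3). An SAE whose causality cannot be assigned within 24 hours gets expedited reporting (Section 7.2.4). Section 8.9 reports SAEs descriptively, by treatment received, and a causality rating does not change the SAE count. None of this supplies a second rating when the CI rates first.

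**Stronger readings the documents do not support.** A reader might infer that the CI rates SAEs in patients the CI operated on. Section 5.2 refers to seven consultants without saying that the CI is among them, and the names in Section 11.6 are removed. All that can be said is that no rule excludes it. A reader might also infer from Section 7.2.2 that the CI decides which routine events count, since listed events go unreported "unless in the opinion of the CI are untoward, excessive, or outside of what might normally be expected for the procedure". There the CI's opinion serves to bring listed events into reporting. Events meeting the SAE definition are reportable regardless, and abnormal pain or bruising is left to the treating clinical team.

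**The shift sizes are hypothetical.** True. The shading would also have to run the same way across seven surgeons and their anaesthetic colleagues.

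**Conclusion.** The concern holds in two parts of unequal strength.

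- **Firm:** Section 11.6 is wrong as written. A secondary outcome, blood loss, is a subjective estimate by teams who know the allocation. This rests on the text alone.
- **Smaller and partly inferred:** SAE causality may be rated by someone who operated on the participant, with no second assessment when the CI is the first rater. That the CI is a surgeon is implied by Section 6.8, not stated; that the CI performs trial operations is not stated at all.

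The primary outcome, OARS at 6 weeks, is completed by participants and is untouched. The consequence is confined to how a blood-loss difference and a pattern of related events may be read, and to the accuracy of a conflict-of-interest statement. The size of any bias is unknown; the false-positive figures hold only under the assumed shifts. The correction should be made because it is cheap and the present statement would mislead.

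**What to change.** 1. **Section 11.6.** Replace the unqualified statement with one naming what the surgical team does determine, including the blood-loss estimate. Report blood loss as an outcome assessed unblinded and interpret it accordingly. Another source within theatre would not restore blinding, so disclosure is the remedy.
2. **Sections 7.2.4 and 7.3.** State that SAE causality is rated by an existing authorised delegate who did not operate on that participant and has not been told the allocation. State also that, if the CI was the operating surgeon, the CI does not give the sole rating. This fits existing arrangements: the delegate role is already defined, the operation note already conceals the technique (Section 6.6), and the rule that the CI may only upgrade a delegate's rating can stay.

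The cost is protocol wording and reassigning a sign-off among existing staff, with no new procedures or data. The small downside is that causality sign-off may be slightly slower within the 24-hour limit.
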